### **2.2.2. Secondary Endpoints**

- Change and percentage change in spleen volume from baseline through Week 24 as measured by MRI (or CT scan in applicable subjects).
- Change and percentage change in total symptom score from baseline through Week 12 or Week 24 as measured by the Myelofibrosis Symptom Assessment Form version 3.0 (MFSAF v3.0) symptom diary and by the Myeloproliferative Neoplasms Symptom Assessment Form (MPN-SAF).
- Number of subjects with responses according to the 2013 IWG consensus criteria for treatment response in PMF, PPV-MF, and PET-MF.
- Patient Global Impression of Change score at each visit where the variable is measured.
- Population PK parameters of INCB050465 and ruxolitinib alone and in combination (eg, AUC, Cmax) will be summarized.
- Safety and tolerability of the treatment regimens through assessment of AEs and changes in safety assessments including laboratory parameters.

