## APPENDIX I. INTERNATIONAL WORKING GROUP— MYELOPROLIFERATIVE NEOPLASMS RESEARCH AND TREATMENT CRITERIA

Response Categories	Required Criteria (for All Response Categories, Benefit Must Last for $\geq$ 12 Weeks to Qualify as a Response)
CR	Bone marrow a : Age-adjusted normocellularity; < 5% blasts; $\leq$ Grade 1 MF b and
	Peripheral blood: Hemoglobin $\geq$ 100 g/L and < UNL; neutrophil count $\geq 1 \times 10^9/L$ and < UNL;
	Platelet count $\geq 100 \times 10^9/L$ and < UNL; < 2% immature myeloid cells c and
	Clinical: Resolution of disease symptoms; spleen and liver not palpable; no evidence of EMH
PR	Peripheral blood: Hemoglobin $\geq$ 100 g/L and < UNL; neutrophil count $\geq 1 \times 10^9/L$ and < UNL; platelet count $\geq 100 \times 10^9/L$ and < UNL; < 2% immature myeloid cells c and
	Clinical: Resolution of disease symptoms; spleen and liver not palpable; no evidence of EMH or
	Bone marrow: a Age-adjusted normocellularity; < 5% blasts; $\leq$ Grade 1 MF b ; and peripheral blood: hemoglobin $\geq 85$ g/L but < 100 g/L and < UNL; neutrophil count $\geq 1 \times 10^9/L$ and < UNL; platelet count $\geq 50 \times 10^9/L$ but < $100 \times 10^9/L$ and < UNL; < 2% immature myeloid cells c and
	Clinical: Resolution of disease symptoms; spleen and liver not palpable; no evidence of EMH
CI	The achievement of anemia, spleen or symptoms response without progressive disease or increase in severity of anemia, thrombocytopenia, or neutropenia d
Anemia response	Transfusion-independent patients: a $\geq 20$ g/L increase in hemoglobin level e
	Transfusion-dependent patients: becoming transfusion-independent f
Spleen response g	A baseline splenomegaly that is palpable at 5-10 cm, below the LCM, becomes not palpable h or
	A baseline splenomegaly that is palpable at > 10 cm, below the LCM, decreases by $\geq 50\%$ h
	A baseline splenomegaly that is palpable at < 5 cm, below the LCM, is not eligible for spleen response
	A spleen response requires confirmation by MRI or CT showing $\geq 35\%$ spleen volume reduction
Symptoms response	A $\geq 50\%$ reduction in the MPN-SAF TSS i
Progressive disease j	Appearance of a new splenomegaly that is palpable at least 5 cm below the LCM or
	A $\geq 100\%$ increase in palpable distance, below LCM, for baseline splenomegaly of 5-10 cm or

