- d See above for definitions of anemia response, spleen response, and progressive disease. Increase in severity of anemia constitutes the occurrence of new transfusion dependency or a  $\geq 20$  g/L decrease in hemoglobin level from pretreatment baseline that lasts for at least 12 weeks. Increase in severity of thrombocytopenia or neutropenia is defined as a 2-grade decline, from pretreatment baseline, in platelet count or absolute neutrophil count, according to the CTCAE version 4.0. In addition, assignment to CI requires a minimum platelet count of  $\geq 25,000 \times 10^9/L$  and absolute neutrophil count of  $\geq 0.5 \times 10^9/L$ .
- e Applicable only to patients with baseline hemoglobin of  $< 100$  g/L. In patients not meeting the strict criteria for transfusion dependency at the time of study enrollment (see as follows), but have received transfusions within the previous month, the pretransfusion hemoglobin level should be used as the baseline.
- f Transfusion dependency before study enrollment is defined as transfusions of at least 6 units of PRBCs, in the 12 weeks prior to study enrollment, for a hemoglobin level of  $< 85$  g/L, in the absence of bleeding or treatment-induced anemia. In addition, the most recent transfusion episode must have occurred in the 28 days prior to study enrollment. Response in transfusion-dependent patients requires absence of any PRBC transfusions during any consecutive "rolling" 12-week interval during the treatment phase, capped by a hemoglobin level of  $\geq 85$  g/L.
- g In splenectomized patients, palpable hepatomegaly is substituted with the same measurement strategy.
- h Spleen or liver responses must be confirmed by imaging studies where a  $\geq 35\%$  reduction in spleen volume, as assessed by MRI or CT, is required. Furthermore, a  $\geq 35\%$  volume reduction in the spleen or liver, by MRI or CT, constitutes a response regardless of what is reported with physical examination.

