7.4.3. Analysis of IWG-MRT Consensus Criteria

IWG-MRT criteria provides criteria for response to treatment in MF. Recently published response criteria developed by the IWG on MF will be used in this study ([Tefferi et al 2013](#)). Overall response assessment will be graded according to the IWG-MRT consensus criteria for treatment response in PMF, PPV-MF, and PET-MF. The criteria for response assessment according to IWG-MRT is provided in [Appendix B](#).

The IWG-MRT assessment will be performed at baseline, Week 24, and every 24 weeks thereafter. The number of participants with responses according to investigator-reported IWG-MRT consensus criteria will be summarized by treatment group. Best overall response under the IWG-MRT consensus criteria will also be summarized. Best overall response is defined as the highest overall response achieved postbaseline prior to and including the first confirmed progressive disease in the order of complete response, partial response, clinical improvement, stable disease, partial disease, and relapse. A listing of the clinical data used by Incyte to derive the IWG-MRT responses will be provided.

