	A 50% increase in palpable distance, below LCM, for baseline splenomegaly of $>$ 10 cm or
	Leukemic transformation confirmed by a bone marrow blast count of \geq 20% or
	A peripheral blood blast content of \geq 20% associated with an absolute blast count of $\geq 1 \times 10^9/L$ that lasts for at least 2 weeks
Stable disease	Belonging to none of the above-listed response categories
Relapse	No longer meeting criteria for at least CI after achieving CR, PR, or CI, or
	Loss of anemia response persisting for at least 1 month or
	Loss of spleen response persisting for at least 1 month

CI = clinical improvement; CR = complete response; CT = computed tomography; EMH = extramedullary hematopoiesis; LCM = left costal margin; MF = myelofibrosis; MPN-SAF TSS = Myeloproliferative Neoplasm Symptom Assessment Form Total Symptom Score; MRI = magnetic resonance imaging; PR = partial response; PRBC = packed red blood cell; UNL = upper normal limit.

- ^a Baseline and post-treatment bone marrow slides are to be interpreted at 1 sitting by a central review process. Cytogenetic and molecular responses are not required for CR assignment.
- ^b Grading of MF is according to the European classification (Thiele et al 2005). It is underscored that the consensus definition of a CR bone marrow is to be used only in those patients in which all other criteria are met, including resolution of leukoerythroblastosis. It should also be noted that it was a particularly difficult task for the working group to reach a consensus regarding what represents a complete histologic remission.
- ^c Immature myeloid cells constitute blasts + promyelocytes + myelocytes + metamyelocytes + nucleated red blood cells. In splenectomized patients, $<$ 5% immature myeloid cells is allowed.
- ^d See above for definitions of anemia response, spleen response, and progressive disease. Increase in severity of anemia constitutes the occurrence of new transfusion dependency or a \geq 20 g/L decrease in hemoglobin level from pretreatment baseline that lasts for at least 12 weeks. Increase in severity of thrombocytopenia or neutropenia is defined as a 2-grade decline, from pretreatment baseline, in platelet count or absolute neutrophil count, according to the CTCAE version 4.0. In addition, assignment to CI requires a minimum platelet count of $\geq 25,000 \times 10^9/L$ and absolute neutrophil count of $\geq 0.5 \times 10^9/L$.

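### The platelet floor for clinical improvement in both copies of the IWG-MRT criteria is 1,000 times too large for its unit, so no subject could be assigned clinical improvement as written

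*Protocol*

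**What the plan says.** IWG-MRT response is a secondary endpoint. Protocol Section 2.2.2 lists it as "Number of subjects with responses according to the 2013 IWG consensus criteria for treatment response in PMF, PPV-MF, and PET-MF". Protocol Section 7.6.8 takes the definitions from Appendix I, and SAP Section 7.4.3 takes them from SAP Appendix B; both sections also cite the 2013 consensus report.

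Both appendices define CI as "The achievement of anemia, spleen or symptoms response without progressive disease or increase in severity of anemia, thrombocytopenia, or neutropenia", with a pointer to footnote d. In the SAP that footnote reads: "assignment to CI requires a minimum platelet count of $\geq 25,000 \times 10^9/L$ and absolute neutrophil count of" 0.5 x 10^9/L or more. The Protocol footnote likewise says that "assignment to CI requires a minimum platelet count of" the same number in the same unit.

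The other platelet limits in the table are on an ordinary scale. Complete response needs "Platelet count $\geq 100 \times 10^9/L$ and < UNL". The bone-marrow route to partial response needs "platelet count $\geq 50 \times 10^9/L$ but < $100 \times 10^9/L$ and < UNL".

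Two outputs draw on the criteria. For the summary tables, SAP Section 7.4.3 says: "The number of participants with responses according to investigator-reported IWG-MRT consensus criteria will be summarized by treatment group". For the sponsor's own derivation it says: "A listing of the clinical data used by Incyte to derive the IWG-MRT responses will be provided". Appendix A of the SAP plans this as Listing 2.6.3.

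**The concern.** CI is the lesser response category, yet its platelet floor stands far above the floors for complete and partial response. That reverses the order of the table and puts CI out of reach. The footnote is part of the operative definition in both documents, and nothing else in either document corrects it.

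A derivation programmed faithfully to the written specification would return no CI in any group. If the programmer quietly corrected the figure, the derivation would depart from its specification without a record. If investigators corrected it in their heads and the program did not, the investigator-reported tables and the sponsor-derived listing would disagree for a reason unrelated to the patients.

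The relapse definition is exposed as well. One of its conditions is that a subject who had responded no longer qualifies for CI or better. With CI unattainable, a subject who slips from complete or partial response but keeps a lesser response would count as relapsed.

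**Working it through.** There is no sample size, power or error rate to reproduce here. The check is a unit conversion and a comparison with the other platelet limits.

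**Inputs, all in 10^9/L**

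- CI floor: 25,000 (Protocol Appendix I and SAP Appendix B, footnote d).
- Complete-response floor: 100 (same table).
- Partial response, marrow route: 50 to below 100 (same table).
- Exclusion below 50, crossover at 50 or more (Protocol Sections 3.3 and 5.2.3).
- Ruxolitinib platelet bands: 50 and 100 (Protocol Table 2, footnote a). Interruption bands: 50 and 75 (Protocol Table 5).
- Grade 3 platelets 25 to below 50 and Grade 4 below 25, so the Grade 3/4 boundary is 25 (Protocol Table 7).
- Neutrophils in Table 7: Grade 3 is 0.5 to below 1.0, so the Grade 3/4 boundary is 0.5.

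**Conversion.** 1 x 10^9/L = 1,000 per microlitre. So 25,000 x 10^9/L = 25,000 x 1,000 = 25,000,000 per microlitre, whereas 25 x 10^9/L = 25,000 per microlitre.

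**Ratio of the stated floor to the other limits**

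| Limit | 10^9/L | 25,000 / limit |
|---|---|---|
| Complete-response floor | 100 | 250 |
| Partial-response floor, marrow route | 50 | 500 |
| Grade 3/4 boundary, Table 7 | 25 | 1,000 |

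**Is the literal value attainable?** The documents give no platelet volume. Assume a mean of 7 to 12 fL. Platelets would then occupy 25,000 x 10^9 per litre x 7 x 10^-15 L = 0.175 of blood volume at the low end, and 25,000 x 10^9 x 12 x 10^-15 = 0.30 at the high end. No patient has a count of this order. The comparison with the other limits gives the same answer without this assumption.

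**What the documents suggest was meant.** The same sentence sets a neutrophil floor of 0.5 x 10^9/L, which is exactly the Grade 3/4 boundary in Table 7. A platelet floor of 25 x 10^9/L would be the matching platelet boundary. It would also lie below the partial-response (50) and complete-response (100) floors, as a lesser category should. Writing 25,000 per microlitre with the other unit attached produces exactly the printed figure: 25,000 / 25 = 1,000.

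**The case against.** The best case on the other side is that this is a recognisable slip with little effect. Most of that stands.

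- **A reader might infer that the reported CI rate will be 0% in every group.** The documents do not support this. The planned summaries (SAP Tables 2.2.10.1 and 2.2.11.1) use investigator-reported responses, and an investigator is unlikely to demand 25 million platelets per microlitre. Appendix A lists no summary table of the sponsor-derived response.
- **A reader might infer that subjects who miss CI fall into stable disease.** This is not certain. Stable disease is the residual class for subjects in none of the listed categories. Anemia, spleen and symptoms response have their own rows in the table, without footnote d. A literal reading leaves the classification of such a subject unclear.
- **That the listing will be coded from the appendix is an inference.** SAP Section 7.4.3 points to Appendix B but also cites the 2013 report, so a programmer has a second reference, and a criterion that every subject fails would be noticed.
- **No inference depends on it.** Protocol Section 9.4.1.2 only tabulates IWG response. The primary spleen-volume analysis, the symptom-score comparisons and the futility rule do not use this footnote.

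These points limit the consequences but not the error. Two controlled documents contain a threshold that cannot be met, in the definition that each names as operative. The identical text in both, outside any amendment log, makes a text-extraction fault unlikely.

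**Conclusion.** The CI platelet floor is wrong as written in both documents: 250 to 1,000 times the other platelet limits, and exactly 1,000 times the value that fits the rest of the plan. Applied literally, CI has no possible members and the CI-dependent part of the relapse definition is distorted.

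The most exposed output is Listing 2.6.3, if it is coded as written. The investigator-reported tables are at risk only under literal application by investigators, which is unlikely. Complete and partial response have their own attainable platelet limits, and the primary analysis is untouched. This is a small correction to a secondary endpoint and no threat to the trial's main conclusion.

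That the figure is wrong follows from the documents alone. That 25 x 10^9/L was intended is an inference from Table 7 and the paired neutrophil floor; the cited 2013 criteria were not available for this check.

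**What to change.** Correct either the number or the unit in footnote d of Protocol Appendix I and of SAP Appendix B, so that the floor is on the scale used elsewhere. The candidate is 25 x 10^9/L, which is the same as 25,000 per microlitre. Confirm it against the cited 2013 criteria before programming the derived response.

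The edit is one line in each document. A Protocol change also needs sponsor and IRB/IEC approval (Protocol Section 10.1), which may be disproportionate in a study that SAP Section 5.2 describes as terminated early. In that case, correct at least the SAP and the programming specification, since these govern Listing 2.6.3, and record the correction in SAP Section 10.

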## APPENDIX J. PROTOCOL AMENDMENT SUMMARY OF CHANGES

Document	Date
Amendment (Version) 1:	13 APR 2016
Amendment (Version) 2:	18 MAY 2016
Amendment (Version) 3:	22 NOV 2016
Amendment (Version) 4:	06 JUN 2017
Amendment (Version) 5:	23 MAR 2018
Amendment (Version) 6:	11 OCT 2018

### Amendment 6 (11 OCT 2018)

#### Overall Rationale for the Amendment:

The purpose of this amendment is to add Part 4 to the study. Part 4 will examine the role an initial higher dose may play in overall efficacy and safety. There are 2 groups in Part 4:

- TG5I/M: 20 mg QD for 8 weeks followed by 5 mg QD until EOT
- TG5D: 5 mg QD from Day 1 until EOT

1. **Synopsis; Section 1.7, Justification of Study Treatment Regimen; 1.8.3, Potential Benefits of INCB050465 Based on Prior and Ongoing Clinical Studies; Section 2, Study Objectives and Endpoints; Section 4.1, Overall Study Design; Section 4.3.1, Planned Number of Subjects; Section 5, Treatment**

**Description of change:** Added Part 4, which will compare a group of subjects who receive an initial higher dose of INCB050465 20 mg QD for 8 weeks followed by 5 mg QD with a group who will receive 5 mg QD from Day 1. Further enrollment into Part 3 is suspended effective with site-specific IRB approval of Amendment 6.

**Rationale for change:** To examine the role an initial higher INCB050465 dose may play in overall efficacy and safety.

2. **Synopsis; Section 4.1, Overall Study Design; Section 5.2.2, Part 2, Part 3, and Part 4 Treatment Groups: Randomized Portion**

**Description of change:** Simplified the description of the 4 parts of the study and indicated that Parts 2 and 3 are no longer enrolling subjects.

**Rationale for change:** To simplify and remove redundant language and to clarify that Parts 2 and 3 are no longer enrolling.

3. **Synopsis; Section 5.2.3, Crossover of Part 2 and Part 3 Subjects**

**Description of change:** Described how subjects randomized to TG20 in Part 3 may cross over to receive INCB050465 5 mg QD once they have reached Week 8.

**Rationale for change:** To provide criteria for Part 3 subjects to cross over.

#### 4. Synopsis; Section 9.4.1, Efficacy Analysis

**Description of change:** Changed treatment group comparisons from all ITT subjects in TG5 and TG20 groups in Parts 2 and 3 to TG5D and TG5I/M + TG5 groups in Parts 3 and 4.

**Rationale for change:** Updated analysis for new treatment groups.

#### 5. Synopsis; Section 9.5.2, Interim Efficacy Analysis

**Description of change:** Updated to include subjects in TG5I/M and TG5D in Part 4. Note that TG5 subjects from Part 3 will also be included in the TG5I/M group.

**Rationale for change:** Updated analysis for new treatment groups.

#### 6. Section 1.5.4, Clinical Summary

**Description of change:** Updated clinical information for INCB050465.

**Rationale for change:** To provide updated information and alignment with the current Investigator's Brochure.

#### 7. Section 1.6, Overview of Ruxolitinib

**Description of change:** Updated information on ruxolitinib safety data in healthy volunteers and MF patients.

**Rationale for change:** To simplify and provide updated information consistent with the current Investigator's Brochure.

#### 8. Section 1.8.2, Potential Risks of INCB050465 Based on Prior Clinical Studies

**Description of change:** Deleted information regarding potential phototoxicity.

**Rationale for change:** Phototoxicity studies have been conducted and did not show any phototoxicity.

#### 9. Appendix B, Cytochrome P450 Inhibitors and Inducers

**Description of change:** Replaced old table of inducers and inhibitors with a new one.

**Rationale for change:** To provide updated information for investigators.

#### 10. Incorporation of administrative changes.

Other minor, administrative changes have been incorporated throughout the Protocol and are noted in the redline version of the amendment.

## **Amendment 5 (23 MAR 2018)**

### **Overall Rationale for the Amendment:**

The purpose of this amendment is to add Part 3 to the study in order to compare INCB050465 20 mg QD for 8 weeks followed by 20 mg once weekly versus INCB050465 20 mg QD for 8 weeks followed by 5 mg QD. As of March 2018, with approximately 25 total subjects treated with the once-weekly dosing frequency in Parts 1 and 2, no DLTs have been observed, and no trends for late onset toxicity have been noted using available nonverified data. There does not appear to be a meaningful difference between the 10 mg and 20 mg dose groups for safety or efficacy. Therefore, it is reasonable to simplify the dosing regimen so that all patients begin receiving INCB050465 at 20 mg QD with comparison between different long-term dose strategies.

- 1. Synopsis; Section 1.7.2, Potential Risks of INCB050465 Based on Prior Clinical Studies; Section 2, Study Objectives and Endpoints; Section 4.1, Overall Study Design; Section 5, Treatment**

**Description of change:** Added Part 3, which compares dose regimens for long-term administration of INCB050465. Further enrollment into Part 2 is suspended effective with site-specific IRB approval of Amendment 5.

**Rationale for change:** Part 3 will explore 2 dose options beyond 8 weeks.

- 2. Synopsis; Section 1.7.2, Potential Risks of INCB050465 Based on Prior Clinical Studies; Section 4, Investigational Plan; Section 5, Treatment; Section 9, Statistics**

**Description of change:** Added designations for dose groups: TG10 (10 mg QD × 8 weeks followed by 10 mg once weekly), TG20 (20 mg QD × 8 weeks followed by 20 mg once weekly), and TG5 (20 mg QD × 8 weeks followed by 5 mg QD).

**Rationale for change:** To simplify the Protocol sections discussing dose groups.

- 3. Synopsis; Section 4.1, Overall Study Design; Section 5.2.1, Part 1: Safety Run-In Portion**

**Description of change:** Add wording to indicate Part 1 has been completed. Change tense for enhanced readability.

**Rationale for change:** Part 1 was completed.

- 4. Synopsis; Section 5.2.3, Crossover of Part 2 Subjects to Part 3**

**Description of change:** Described how subjects randomized to 10 mg in Part 2 may cross over to Part 3 doses.

**Rationale for change:** To provides criteria for Part 2 subjects to cross over to Part 3.

- 5. Synopsis; Section 4.4, Duration of Treatment and Subject Participation; Section 6, Study Assessments (Table 8, Schedule of Assessments); Section 6.1, Screening**

**Description of change:** Change screening windows from Day -28 to Day -8 to Day -35 to Day -8 (increases period from 21 days to 28 days)

**Rationale for change:** A 28-day screening period is consistent with other protocols.

**6. Section 6, Study Assessments (Table 11, Schedule of Pharmacokinetic Sampling for Part 1, Part 2, and Part 3)**

**Description of change:** Added footnotes.

**Rationale for change:** To provide windows for sample collection and fasting details.

**7. Synopsis; Section 9.4.1, Efficacy Analysis**

**Description of change:** Changed treatment group comparisons from all ITT subjects in Part 2 to TG5 and TG20 subjects in both Parts 2 and 3.

**Rationale for change:** Updated analysis for new treatment groups.

